7.5.21. By Gender Analyses

The aim of the following analyses is to examine gender effect in various key endpoints. The methodology will use the pre-specified models for each key endpoint while introducing gender and treatment by gender interaction. Corresponding contrasts will be created to test the treatment effect in males and females.

- Repeat the primary endpoint of Brain Atrophy as measured by Percent Brain Volume Change (PBVC) at week 48 by gender. This analysis will be performed on the mITT1 analysis set and will use the primary analysis model while adding gender and treatment by gender interaction terms. SAS code as example is specified below

```
PROC MIXED;
  CLASS SUBJID ARM WEEK CGR GENDER;
  MODEL BA= NBVBASE LT2BASE CGR ARM|WEEK|GENDER / SOLUTION CL;
  REPEATED WEEK / TYPE=UN SUBJECT=SUBJID R RCORR;
  LSMEANS ARM*WEEK*GENDER / PDIFF CL;
  LSMESTIMATE TRTPN*WEEK*GENDER "MALES, WEEK 48, 0.6 MG VS PLACEBO" [-1, 1 2 1] [1, 2 2 1]/CL;
  LSMESTIMATE TRTPN*WEEK*SUBVAR "FEMALES, WEEK 48, 0.6 MG VS PLACEBO" [-1, 1 2 2] [1, 2 2 2]/CL;
  WHERE ARM in ('Laquinimod 0.6 mg', 'Placebo') and mITT1='Y' ;
  RUN;
```

- Repeat the first secondary of Time to CDP as measured by EDSS by gender. This analysis will be performed using the ITT analysis set and will use the time to CDP measured by EDSS model together while adding gender and gender by treatment interaction terms as shown in the SAS code below.

```
PROC PHREG;
  CLASS ARM EDSSBASE CGR GENDER;
```

```

MODEL TIME_TO_PROGRESSION*CENSOR(1,2,3)=ARM GEMDER ARM * GENDER EDSSBASE AGE
LT2BASE CGR /COVB RL;
CONTRAST "MALES , 0.6 MG VS PLACEBO "  ARM 1 GENDER 0  ARM * GENDER 1 /ESTIMATE=EXP ;
CONTRAST "FEMALES 0.6 MG VS PLACEBO "  ARM 1 GENDER 0  ARM * GENDER 0 /ESTIMATE=EXP;
WHERE ARM in ('Laquinimod 0.6 mg', 'Placebo');
RUN;

```

- Repeat the second secondary of Time to CDP as measured by EDSS or T25FW by gender. This analysis will be performed using the ITT analysis set and will use the time to CDP measured by EDSS or T25FW model while adding with gender and gender by treatment interaction terms as shown for the first secondary endpoint of time to CDP measured by EDSS.
- Repeat the third secondary endpoint of change from baseline to week 48 in the T25FW test by gender. This analysis will be performed on the mITT2 analysis set and will use the original ranked model while adding gender and treatment by gender interaction terms.

```

PROC MIXED DATA=RANKED;
CLASS SUBJID ARM WEEK CGR;
MODEL CHANGERANK= T25BASERANK CGR ARM|WEEK|GENDER;
REPEATED WEEK / TYPE=UN SUBJECT=SUBJID R RCORR;
LSMEANS ARM*WEEK*GENDER / PDIFF CL;
LSMESTIMATE arm*WEEK*GENDER "MALES, WEEK 48, 0.6 MG VS PLACEBO" [-1, 1 2 1] [1, 2 2 1]/CL;
LSMESTIMATE arm*WEEK* GENDER "FEMALES, WEEK 48, 0.6 MG VS PLACEBO" [-1, 1 2 2] [1, 2 2 2]/CL;
RUN;

```

- Repeat the for the secondary endpoint of number of new T2 lesions at week 48 by gender. This analysis will be performed on the mITT2 analysis set and will use the original GENMOD model while adding gender and treatment by gender interaction terms.

```

PROC GENMOD;
CLASS ARM CGR GENDER;
MODEL T2LES=ARM GENDER ARM * GENDER LT2BASE AGE CGR/ DIST=NB LINK=LOG TYPE3;
LSMEANS ARM*GENDER/ CL;
lsmESTIMATE arm*gender "MALE 0.6 MG VS PLACEBO "  [-1, 1 1] [1, 2 1]/exp;
lsmESTIMATE arm*gender "FEMALE 0.6 MG VS PLACEBO "  [-1, 1 2] [1,2 2]/exp;
WHERE ARM in ('Laquinimod 0.6 mg', 'Placebo');
RUN;

```

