### 9.2. Sample Size and Power Considerations

Sample size calculations were based on the following assumptions:

- 2-sided alpha level of 5%
- treatment difference (delta) of 0.3 in PBVC
- standard deviation of 0.8

Under the above assumptions 252 patients enrolled for 0.6 mg and placebo (126 per arm) will provide 84% power to detect a statistically significant result for 0.6 mg laquinimod arm comparison to placebo. To adjust for the anticipated 10% dropouts, the sample size was increased to 280 patients. Adding 95 patients on 1.5 mg yields a total of 375 patients.

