Statistical Analysis Plan

A Multinational, Multicenter, Randomized, Double-Blind, Parallel-Group, Placebo-Controlled Study to Evaluate the Efficacy, Safety, and Tolerability of Once Daily Oral Administration of Laquinimod (0.6 or 1.5 mg) in Patients with Primary Progressive Multiple Sclerosis (PPMS)

Study TV5600-CNS-20006

(ARPEGGIO - A Randomized Placebo-controlled trial Evaluating laquinimod in PPPMS, Gauging Gradations In MRI and clinal Qoutcomes)

NCT02284568

Date: June 2017

TEVA BRANDED PHARMACEUTICAL PRODUCTS R&D, INC.
STATISTICAL ANALYSIS PLAN

**A Multinational, Multicenter, Randomized, Double-Blind, Parallel-Group,
Placebo-Controlled Study to Evaluate the Efficacy, Safety, and Tolerability of Once Daily
Oral Administration of Laquinimod (0.6 or 1.5 mg) in Patients with Primary Progressive
Multiple Sclerosis (PPMS)**

Study TV5600-CNS-20006 (ARPEGGIO - A Randomized Placebo-controlled trial Evaluating laquinimod in PPMS, Gauging Gradations In MRI and clinical Outcomes)

Phase 2

Date: 2-May-2016

Version: 1.0 Final

Prepared by: [REDACTED]

Version Control

Version No.	Date	Name	Title
1.0 Final	May, 2012	[REDACTED]	[REDACTED]
2.0, Final	June, 2017	[REDACTED]	[REDACTED]

SAP AMENDMENT RATIONALE VERSION 2.0 (JUNE 2017)

Following LAQ-MS-305 (CONCERTO) study results in RRMS, a gender effect was seen as a potential subpopulation for laquinimod treatment to be further explored. The sponsor decided to include a gender subgroup analysis for both the primary and all secondary endpoints.

TABLE OF CONTENTS

TITLE PAGE	1
SAP AMENDMENT RATIONALE VERSION 2.0 (JUNE 2017).....	2
LIST OF ABBREVIATIONS AND DEFINITIONS OF TERMS	7
PREFACE	9
1. SCOPE OF THIS SAP.....	10
2. STUDY OBJECTIVES	11
3. STUDY DESIGN	12
3.1. General Design and Study Schema.....	12
3.2. Primary and Secondary Measures and Endpoints	21
3.2.1. Primary Efficacy Variable and Endpoint.....	21
3.2.2. Secondary Efficacy Variable and Endpoint.....	21
3.2.3. Exploratory Efficacy Variables and Endpoints	21
3.2.4. Other Variables and Endpoints	22
3.2.5. Safety Variables and Endpoints.....	22
3.2.6. Tolerability Variables and Endpoints	22
3.2.7. Pharmacokinetic Variables and Endpoints	23
3.3. Sample Size and Power Considerations	23
3.4. Randomization and Blinding	23
3.5. Sequence of Planned Analyses	23
3.5.1. Interim Analyses.....	23
3.5.2. Final Analyses and Reporting.....	24
4. POPULATIONS /ANALYSIS SETS.....	25
4.1. Intent-to-Treat (ITT) Population.....	25

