3.3. Sample Size and Power Considerations

Sample size calculations were based on the following assumptions:

- 2-sided alpha level of 5%
- treatment difference (delta) of 0.3 in PBVC
- standard deviation of 0.8
- drop-out date of 10%

Under the above assumptions in order to reach power of 80%, 125 patients per arm should be enrolled. Since initially, this study was planned to have 3 treatment arms, the original sample size was 375 patients. Although, the enrollment to 1.5 mg laquinimod arm was stopped as specified in Section 3.1 and included 95 randomized patients, the Sponsor decided to continue enrollment to the laquinimod 0.6 mg and placebo arms until the total sample size reaches the initially planned 375 patients. This will result in 140 patients per arm (lauqinimod 0.6 mg/placebo) which provides 84% power.

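### The by-gender analyses designate separate drug tests in males and females, and name no sex-difference result and no rule for reading one

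*SAP*

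**What the plan says.** The amendment rationale for SAP version 2.0 gives one reason for the change: after another laquinimod study, "a gender effect was seen as a potential subpopulation for laquinimod treatment to be further explored". SAP 7.5.21 states its purpose as "The aim of the following analyses is to examine gender effect in various key endpoints". It adds gender and treatment-by-gender terms to the model for each of the five endpoints and then says: "Corresponding contrasts will be created to test the treatment effect in males and females".

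Every `LSMESTIMATE` or `CONTRAST` statement written out there compares 0.6 mg with placebo in one sex. The composite progression endpoint has no code of its own and follows the EDSS pattern. That makes two within-sex tests for each of five endpoints, and no contrast between the sexes.

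SAP 7.2 handles two other effect modifiers differently. For baseline covariates and for country/region it specifies an interaction test, a threshold of p ≤ 0.10 and what follows if the threshold is met. SAP 13.1 lists a table for the covariate-interaction evaluation (15.16). SAP 13 lists no by-gender table or graph.

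SAP 3.2.3 places all five gender analyses among the exploratory endpoints, and the testing hierarchy in SAP 5.3 does not include them.

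**The concern.** Whether the drug effect differs between men and women is a question about a difference of two effects. The designated tests ask two other questions: is there an effect in men, and is there one in women? Each sex supplies only part of the sample, so each test has much less power than the overall comparison. A drug that works equally well in both sexes can therefore easily reach p < 0.05 in one and miss it in the other.

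The stated interest is a possible treatment subpopulation. If the by-gender output is two p-values per endpoint, with no interaction estimate put forward and no instruction on how to read it, a chance split can pass for a sex-specific effect. It could then shape later development.

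**Working it through.** **Inputs**
- Two-sided alpha 5%, "treatment difference (delta) of 0.3 in PBVC" and "standard deviation of 0.8" (SAP 3.3).
- "252 patients enrolled for 0.6 mg and placebo (126 per arm) will provide 84% power" (Protocol 9.2). The increase to 280 enrolled allows for 10% dropout, so 126 per arm is the evaluable number.
- The sex split is not in the documents. It is assumed, from 50:50 to 30:70, and taken as equal in the two arms.

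**Step 1. Reproduce the plan's figure.** SE = 0.8 × √(2/126) = 0.101. Power = Φ(0.3/0.101 − 1.96) = 84.5%, or 84.3% with the t distribution. The stated 84% is reproduced. The 140 per arm in SAP 3.3 gives 84% only after the 10% dropout; 140 evaluable per arm would give 88.1%.

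**Step 2. Power within each sex, same true effect of 0.3 in both.**
- 50:50, 63 per arm in each sex: SE = 0.8 × √(2/63) = 0.143, power 55.8% (t: 55.1%).
- 30:70, 37.8 and 88.2 per arm: power 37.1% and 70.2%.

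**Step 3. Probability that exactly one sex is significant.** The sexes are independent samples, so this is p₁(1 − p₂) + p₂(1 − p₁).

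| Sex split | Uniform effect 0.3 | 0.15 | 0.2 | 0.4 |
|---|---|---|---|---|
| 50:50 | 49.3% | 29.8% | 41.1% | 31.8% |
| 40:60 | 50.8% | 29.9% | 41.5% | 34.7% |
| 30:70 | 55.2% | 30.4% | 42.7% | 43.0% |

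At 0.3 and 50:50, both sexes are significant in 31.1% of trials and neither in 19.6%. With 140 evaluable per arm, the 0.3 column runs from 47.9% to 54.7%. With no effect at all, at least one sex is significant in 1 − 0.95² = 9.8% of trials per endpoint.

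**Step 4. What an interaction contrast would do.** The SE of the male-minus-female difference in treatment effect is 0.8 × √(2/63 + 2/63) = 0.202 at 50:50 and 0.8 × √(2/37.8 + 2/88.2) = 0.220 at 30:70, against 0.101 overall. Under a uniform effect it is significant 5% of the time. In simulation at 50:50 (1,000,000 draws), a one-sex pattern together with a significant sex difference occurred in 4.8% of trials, against 49% for the one-sex pattern alone.

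**Step 5. What the specified code already prints.**
- PBVC: the model crosses treatment, week and gender and requests `SOLUTION CL`. The contrasts in SAP 7.2 and 7.5.21 put week 48 as the second and last week. With last-level reference coding, the non-reference `ARM*GENDER` coefficient then equals the week-48 difference of differences. It is unlabelled and depends on level order: SAP 7.2 takes drug as the first treatment level and the gender contrasts take it as the second, so even the sign needs care. The Type 3 tests do not replace it. `ARM*GENDER` there averages over weeks, and `ARM*WEEK*GENDER` tests whether the sex difference changes between weeks.
- New T2 lesions: one time point with `TYPE3`, so the `ARM*GENDER` test is the week-48 sex-difference test.
- Both progression endpoints: the Cox models print an `ARM*GENDER` coefficient, the log ratio of hazard ratios.
- T25FW: four weeks, no `SOLUTION` option, and pairwise mean differences only. Nothing gives the week-48 sex difference.

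**The case against.** The strongest reply is that the information is largely there. The plan fits joint interaction models, not separate subgroup models, and for four of the five endpoints the output contains the sex-difference estimate or its test. A reader might infer from the listed contrasts that the interaction is not fitted or cannot be estimated. The documents do not support that: Step 5 shows otherwise, and only T25FW lacks it. For T25FW the model is on ranks, so a difference of differences has no direct clinical scale.

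The plan also does not commit the error. No sentence says a gender effect will be declared when one sex has p < 0.05 and the other does not. The language is of examining and exploring, CIs are requested in the PBVC and T25FW code, and the analyses sit outside the hierarchy. Within-sex estimates also bear on the subpopulation question.

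All of that stands, and it limits the weight of the point. What remains is that a coefficient in a solution table, which the SAP neither names nor assigns a role, is not a designated result. Exploratory status explains the absence of error control. It does not make a comparison of two p-values a valid reading of a difference, and the SAP shows in section 7.2 that it knows how to specify an interaction evaluation.

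**Conclusion.** The point holds as a mismatch between the stated question and the designated tests, with no named sex-difference result and no reading rule. For PBVC at the planned effect, a uniform benefit would show as significant in exactly one sex in about 49% to 55% of trials. This rests on the plan's delta and SD, 126 evaluable per arm, and an assumed sex split.

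A reader might take about half the time as a property of all the by-gender analyses. The documents do not support that. The figure falls to about 30% to 43% for PBVC at uniform effects of 0.15, 0.2 or 0.4, and no planning inputs are given from which to compute it for the secondary endpoints. Nor do these exploratory analyses touch the primary or secondary conclusions. It is an inexpensive improvement that should be made.

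**What to change.** In SAP 7.5.21, make the treatment-by-gender estimate with its 95% CI the main by-gender result, from a labelled contrast:
- PBVC: the week-48 difference of differences.
- T25FW: the same on the rank scale, with a note that it has no direct unit.
- Both progression endpoints: the ratio of hazard ratios.
- New T2 lesions: the ratio of rate ratios.

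Keep the within-sex estimates with CIs as description. Add a sentence that a gender effect is judged from the interaction estimate and not from one significant and one non-significant within-sex test, and list the by-gender outputs in SAP 13.

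The cost is one contrast per endpoint and a few lines of text, with no new data, visits or models. The downside is precision. On PBVC the SE is about twice the overall one, so the 95% CI half-width is about 1.96 × 0.202 = 0.40 points at 50:50. Power is about 32% for a true sex difference of 0.3 and 85% for 0.6. The report should say so, and a non-significant interaction should not be read as proof that the sexes respond alike.

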7.6. Tolerability Variables and Analysis

Tolerability analysis will be performed only for placebo and laquinimod 0.6 mg patients and will be presented by proportion of patients (%) who prematurely discontinued treatment and reason of discontinuation (including early termination due to AEs). Additionally the time to Early Termination (ET) and time to ET due to AEs will be presented by Kaplan-Meier curves. No statistical inference will be done.

All analyses presented in the section will be repeated to include both part A and part B when the study is completed.

8. SAFETY ANALYSIS

8.1. General

The safety population will be used for all safety analyses. Summaries will be presented by treatment group.

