#### **1.4.1.1.4. Back and Neck Pain**

Treatment with laquinimod has been associated with an increased incidence of back and neck pain. Back and neck pains usually occurred during the first 3 months of treatment, were generally of mild severity, but occasionally occurred at a later time point, were of longer duration, or required symptomatic treatment.

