#### **1.4.1.1.7. Cardiovascular Events (on Doses Above Laquinimod 0.6 mg)**

On 30 December 2015, a DMC review of 8 unblinded cases from the ARPEGGIO and CONCERTO studies found an imbalance in serious cardiovascular events in the high dose

treatment arms in the study: 6 cases of myocardial infarction in the CONCERTO 1.2 mg treatment arm, compared to no events in the 0.6 mg or placebo treatment arms, along with a cerebral infarction in a 31-year old man on the 1.2 mg treatment arm. In the ARPEGGIO study, 1 myocardial infarction event was identified in the laquinimod 1.5 mg treatment arm. The decisions were largely based on data from 15 November 2015 when total exposure in CONCERTO was 3070 patient-years in 2199 individuals and total exposure in ARPEGGIO was 35 patient-years in 191 individuals.

Due to these events, the DMC recommended stopping all laquinimod treatment arms above 0.6 mg in the laquinimod MS trials. The DMC did not identify any overt cardiovascular risk in the 0.6 mg treatment arm, but felt that long term monitoring for emergence of any signal was necessary. The DMC also recommend that study subjects continuing on laquinimod 0.6 mg be reconsented with information about the cardiovascular risk seen in higher doses.

Currently the mechanism of the cardiovascular events remains unknown. Although no specific time-to-event patterns have been identified, cardiovascular risk factors and demographics may play a role. Different pre-existing risk factors were noted, including hypertension, high cholesterol, and/or smoking history. While all cases exhibited signs of myocardial tissue injury, the cardiac work-up in these cases revealed heterogeneous etiologies. Of note, the cases all had some established cardiovascular risk factors, including patients with probable myocarditis or with probable familial hypercholesterolemia. Further investigation into potential predictors and the potential causality are ongoing.

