### **3. STUDY DESIGN**

#### **3.1. General Design and Study Schema**

This is a multinational, multicenter, randomized, double-blind, parallel-group, placebo-controlled study, to evaluate the efficacy, safety and tolerability of daily oral administration of laquinimod (0.6 or 1.5 mg) in patients with PPMS.

Prior to 01 January 2016, eligible patients were randomized in a 1:1:1 ratio into 1 of the following treatment arms (a total of 286 patients were randomized 1:1:1 prior to 01 January 2016):

- Laquinimod 0.6 mg daily
- Laquinimod 1.5 mg daily
- Daily placebo

As of 01 January 2016, following a decision to discontinue the laquinimod 1.5 mg dose arm, additional eligible patients who are enrolled will be randomized in a 1:1 ratio into one of the following treatment arms:

- Laquinimod 0.6 mg daily
- Daily placebo

A capped randomization procedure will be employed to ensure that the proportion of EDSS 6.0 and 6.5 patients will not exceed more than 20% of all enrolled patients.

The study will include screening up to 6 weeks and 2 parts: Part A (core study) and Part B (data analysis).

Part A will last at least 48 weeks, and individual patients will experience variable treatment durations, depending on the order of enrollment.

[figure not shown]
Once the last ongoing patient completes the week 48 visit, the sponsor will declare end of Part A and begin performing study analyses.

In Part B, patients will continue their randomly-assigned blinded treatments with visits every 12 weeks until the completion visit. After up to approximately 24 weeks of Part B, or once data analysis has been completed and the design of a potential extension study has been finalized (including blinded or open-label treatment allocation), patients will be invited to the clinic for the completion visit and will be offered the opportunity to continue into an extension study, if applicable.

Patients will have the following study visits: screening visit (-6 weeks), baseline visit (week 0), weeks 4, 8, 12, 24, 36, 48, and every 12 weeks until study completion or early termination (ET).

The study schema is presented in [Figure 1](#) (prior to 01 January 2016) and [Figure 2](#) (from 01 January 2016).

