2. STUDY OBJECTIVES

The objectives of this study are to assess the efficacy, safety, and tolerability of a once daily oral dose of laquinimod (0.6 or 1.5 mg) compared to placebo in PPMS patients.

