3. STUDY DESIGN

3.1. General Design and Study Schema

This is a multinational, multicenter, randomized, double-blind, parallel-group, placebo-controlled study, to evaluate the efficacy, safety and tolerability of daily oral administration of laquinimod (0.6 or 1.5 mg) in patients with PPMS.

On 30 December 2015 the Data Monitoring Committee (DMC) for the CONCERTO and ARPEGGIO studies held an unscheduled meeting to review cardiovascular events. The DMC found an imbalance in serious cardiovascular events in the high dose treatment arms (1.2 mg in CONCERTO, 1.5 mg in ARPEGGIO): in CONCERTO there were 6 such cases in the 1.2 mg arm but none in the 0.6 mg or placebo arms, along with a myocardial infarction in the ARPEGGIO 1.5 mg dose group and a cerebral infarction in a 31-year old patient in the 1.2 mg arm of CONCERTO. Due to these events and the DMC recommendation to stop all laquinimod treatment arms above 0.6 mg in the MS trials, the 1.5 mg treatment arm in the ARPEGGIO study was discontinued as of 01 January 2016.

Prior to 01 January 2016, eligible patients were randomized in a 1:1:1 ratio into 1 of the following treatment arms:

1. Laquinimod 0.6 mg daily
2. Laquinimod 1.5 mg daily- in total 95 patients were randomized to this arm.
3. Daily placebo

As of 01 January 2016, following a decision to discontinue the laquinimod 1.5 mg dose arm, additional eligible patients who are enrolled will be randomized in a 1:1 ratio into one of the following treatment arms:

1. Laquinimod 0.6 mg daily
2. Daily placebo

A capped randomization procedure will be employed to ensure that the proportion of Expanded Disability Status Scale (EDSS) 6.0 and 6.5 patients will not exceed more than 20% of all enrolled patients.

The study will include screening up to 6 weeks and 2 parts: Part A (core study) and Part B (data analysis).

Part A will last at least 48 weeks, and individual patients will experience variable treatment durations, depending on the order of enrollment.

Once the last ongoing patient completes the week 48 visit, the sponsor will declare end of Part A and begin performing study analyses.

[figure not shown]

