8.3. Adverse Events

All adverse events (AEs) will be coded using MedDRA. Summaries will be presented for all adverse events (overall and by severity), adverse events determined by the investigator to be treatment-related (overall and by severity), serious adverse events, adverse events causing discontinuation of the study drug, non-serious adverse events, and adverse events by outcome. The AEs will be presented by system organ class and preferred term. Each summary will include number of patients who experienced at least one AE within each category and corresponding percentage from the ST population, number of adverse events within each category and corresponding event rate. For incidence, patients will be counted only once in each system organ

class category and only once in each preferred term category. For frequency in cases when more than one AE with the same preferred term (PT) started on the same date for the same patient, these will be considered as duplicates and will be counted as one AE for that patient. If onset date of AEs with the same PT is partially unknown, then these AEs will be counted as separate AEs. An event rate will be defined as the total number of AEs divided by total exposure to study drug in patient years. Treatment-related adverse event summaries will include adverse events with missing relationship to study drug.

For the summaries by severity, for incidence patients are counted at the greatest severity, and for frequency when cases with duplicate AEs appear, the greatest severity will be assigned for that AE. Adverse events missing the flag indicating serious will be excluded from the summary of serious adverse events but included in the summary of non serious adverse events. For the summary by outcome, for incidence patients are counted at their worst outcome and for frequency when cases with duplicate AEs appear, the worst outcome will be assigned for that AE.

Treatment emergent AEs only which happened under study treatment will be included for all summaries and are defined as events with onset between (including) the date of first study drug dose , up to seven days after the date of last study drug dose. In addition, a summary of all AEs that happened following seven days after the last dose of the study drug will be presented as well.

All analyses presented in the section will be repeated to include both part A and part B when the study is completed.

All AEs will be presented in patient data listings.

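### The 1.5 mg safety tables use neither a common time window nor concurrent placebo, so crude percentages and any-time tables understate 1.5 mg risk relative to placebo for events that accrue with time on drug

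*SAP*

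**What the plan says.** The objective in SAP 2 is "to assess the efficacy, safety, and tolerability of a once daily oral dose of laquinimod (0.6 or 1.5 mg) compared to placebo".

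SAP 3.1 records that 1.5 mg was discontinued as of 01 January 2016 and that "in total 95 patients were randomized to this arm". Protocol 3.1 adds that "a total of 286 patients were randomized 1:1:1 prior to 01 January 2016". Later patients were randomised 1:1 to 0.6 mg or placebo. Part A runs until the last ongoing patient reaches week 48, and SAP 3.3 expects 140 patients on each of 0.6 mg and placebo.

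SAP 5.1 makes 1.5 mg descriptive only, citing its low exposure, and limits non-MRI data to 7 days after the last dose. For safety, SAP 8.1 states: "The safety population will be used for all safety analyses. Summaries will be presented by treatment group". It sets no common window and no concurrent comparator.

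Each adverse-event summary in SAP 8.3 gives patients and percentages of the safety population, the number of events, and a rate: "An event rate will be defined as the total number of AEs divided by total exposure to study drug in patient years". The following have no exposure adjustment:

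- abnormal and potentially clinically significant (PCSA) laboratory incidence, any-time laboratory shifts, and maximum AST, ALT and GGT (SAP 8.5)
- vital-sign PCSA incidence (SAP 8.6)
- any-time QTc shifts (SAP 8.7)

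SAP 7.6 restricts the tolerability analysis to placebo and 0.6 mg.

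**The concern.** A percentage of patients with at least one event rises with time on drug. If one arm has about a quarter of the other's time, the two percentages are not comparable. Dividing by patient-years helps only if events arrive at a roughly steady rate. The protocol describes several reactions that do not: back and neck pain "usually occurred during the first 3 months of treatment" (1.4.1.1.4), liver enzyme rises came mostly within 6 months (1.4.1.1.1), and the haemoglobin fall came early (1.4.1.1.6).

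Concurrency is a separate matter. Amendment 02, issued after the stop, added troponin testing when CPK is raised, a dedicated form for ischaemic events, cardiovascular risk management, and renal and hepatic stopping rules (Protocol 17.1). Later placebo time therefore differs from 1.5 mg time in how events are detected and managed, and no rate calculation removes that.

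At stake is the only randomised, concurrent safety comparison of 1.5 mg in this trial. It serves a stated objective, and no planned table displays it.

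**Working it through.** **1. Arm sizes (the plan's own figures).** 286/3 = 95.3, against 95 stated for 1.5 mg. Before the stop, the other two arms hold (286 − 95)/2 = 95.5 each. After it they gain (375 − 286)/2 = 44.5 each. The sum is 140, as in SAP 3.3. The share of placebo randomised after the stop is 44.5/140 = 31.8%.

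**2. Mean exposure at the stop.** The documents give no figure, so this is an estimate. Protocol 1.4.1.1.7 says that at 15 November 2015 "total exposure in ARPEGGIO was 35 patient-years in 191 individuals", a mean of 35/191 = 0.183 years (9.6 weeks). The stop came 47 days later, by which time 286 − 191 = 95 more patients had been randomised. Assume that the 191 covers all three arms, that nobody stopped early, and that enrolment was even:

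- 35 + 191 × 47/365.25 + 95 × 23.5/365.25 = 35 + 24.6 + 6.1 = 65.7 patient-years
- 65.7/286 = 0.230 years, or 12.0 weeks
- 0.230 × 95 = about 22 patient-years on 1.5 mg

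If the last 95 all joined at the end of the interval, the mean is 10.9 weeks; if all joined at its start, 13.1 weeks. An outer bound, with no enrolment after the November cut, is 35/191 + 47/365.25 = 0.312 years, or 16.3 weeks.

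**3. Events at a constant rate.** Incidence = 1 − exp(−rate × time), with 12 weeks = 0.230 years on 1.5 mg and 48 weeks = 0.920 years on placebo. The placebo rates are illustrative.

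| Placebo rate per year | True hazard ratio | 1.5 mg % | Placebo % | Ratio of patient-year rates |
|---|---|---|---|---|
| 0.1 | 1 | 2.3 | 8.8 | 1 |
| 0.1 | 2 | 4.5 | 8.8 | 2 |
| 0.1 | 4 | 8.8 | 8.8 | 4 |
| 0.5 | 1 | 10.9 | 36.9 | 1 |
| 0.5 | 2 | 20.5 | 36.9 | 2 |
| 0.5 | 4 | 36.9 | 36.9 | 4 |

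The percentages match only when the true hazard ratio equals the exposure ratio: 48/12 = 4, or 48/16.3 = 2.9 at the outer bound. The patient-year rate recovers the true ratio throughout.

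**4. Events confined to the first 12 weeks, with equal risk p.** The percentages agree (p in both arms), but the rate ratio is (p/12)/(p/48) = 4. With an assumed 72 weeks on placebo it is 6. These are limiting values, because some 1.5 mg patients had less than 12 weeks on drug.

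**5. Concurrent cohort, common cut.** Follow-up then has the same distribution in each arm by randomisation, apart from differential early stopping. Equal hazards give an incidence ratio of 1 whether events are early or steady.

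**The case against.** The SAP already provides a good deal. Every adverse-event summary, including serious events and events causing discontinuation, prints the percentage and the rate together, and step 3 shows the rate is right under a constant hazard. Laboratory, vital-sign and ECG results are also summarised by visit, which aligns the arms on time since first dose. SAP 8.2 tabulates exposure in bands, and SAP 5.1 keeps 1.5 mg out of all inference. For the cardiovascular events themselves, Protocol 1.4.1.1.7 reports no particular time pattern. The arm has already been stopped, so no planned test depends on these tables.

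A reader might also infer from SAP 7.6 that 1.5 mg discontinuations go unreported. They do not: SAP 6.2 gives early termination by reason, and SAP 8.3 covers adverse events causing discontinuation. A Kaplan-Meier curve of time to termination on 1.5 mg would mainly show the sponsor's stop, which Protocol 4.3.1 records as the withdrawal reason.

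All of this stands, and it narrows the point. It does not remove it. The percentage and the rate can err in opposite directions in the same table, with nothing to tell the reader which to trust. The rate exists only for adverse events, and it counts all events rather than patients with a first event. The by-visit tables still include placebo patients randomised after the stop, and they do not replace the any-time abnormality tables.

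**Conclusion.** This is a cheap improvement. It does not threaten the trial's efficacy conclusions. Crude adverse-event percentages and the unadjusted any-time tables understate 1.5 mg risk relative to placebo for events that accrue over time, because about 12 weeks of mean exposure is set against a planned 48 or more. The patient-year rate overstates 1.5 mg risk for early reactions.

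A reader might infer that the safety tables as a whole make 1.5 mg look safer than it is. The documents do not support that: the direction depends on the display and on when events occur.

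The size rests on the assumptions in step 2 and on dosing ending on 01 January 2016. The 48 weeks is the plan for placebo patients who stay on drug; the 10% dropout anticipated in Protocol 9.2 lowers the arm mean. Against that, 301 of about 375 patients were enrolled by 01 February 2016 (Protocol, Amendment History), so concurrent placebo patients who continue would exceed 48 weeks.

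Nor would the concurrent cohort settle the cardiovascular question. At the 0.16 events per 100 person-years that Protocol 1.4.2 estimates for 0.6 mg, 22 patient-years gives 22 × 0.0016 = 0.035 expected events per arm.

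**What to change.** Add to SAP 8.1 a supplementary set of tables restricted to the 286 patients randomised 1:1:1 before 01 January 2016, showing all three arms. In every arm, cut data and exposure at 01 January 2016 plus the same 7-day allowance. Include:

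- adverse events, serious adverse events and adverse events causing discontinuation
- laboratory abnormal and PCSA incidence, any-time shifts, and maximum AST, ALT and GGT
- vital-sign PCSA incidence and any-time QTc shifts

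State that any 1.5 mg versus placebo safety statement rests on this set, and keep the full-follow-up tables for 0.6 mg versus placebo. Report the actual 1.5 mg exposure in place of the 12-week estimate. Note that the cohort is too small to inform rare cardiovascular events, which remain in the individual listings.

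The cost is a cohort flag, a cut-off date and a re-run of existing table programs. No new data are needed. The drawback is more tables.
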